#### *2.5 LHA recruitment and training*

A total of 30 people was recruited for LHA training. LHAs are recommended by public health center and tribal community building coordinator as a priority. Selection of LHAs were over 25 years old, indigenous people from the same community, communicated in indigenous language and had a driver license of motorcycle or car. Subsequently, all LHAs received 4-week 15-hour curriculums of training. The training manual was developed to educate the LHAs about association of common oral diseases and systemic diseases in older people, oral care for the older people, teaching principles and methods, working log and practice and final is communication skill. After 4 weeks

of training, 28 trainee LHAs passed the qualification exam and became certified LHAs.

### *2.6 Intervention*

Oral exercise intervention is designed to increase the range of movement in tongue, lips, and jaw as well as salivary gland massages, which will help speech and/or swallow functioning. All participants performed oral exercise before three meals a day, whereas the participants in the EG also received 4 lessons from a LHA over 4 weeks. Four lessons were taught one-on-one once a week by a certified LHA at the participants' homes. The lessons including understand oral structure, learn oral self-care skills and oral function promotion, understand the status of oral self-care and the relationship between oral diseases and systemic diseases, understand swallowing dysfunction and safe eating skills and review. Teaching tool including oral health leaflets, oral exercise video, dental model, magnets, stickers and oral care logbook. The participants in the CG received leaflets only.

[figure not shown]
### *2.7 Data collection*

Data were collected by thoroughly trained interviewers during face-to-face interviews in accordance with standard protocol. Each interviewer attended a 1-hour training course on the standard process and data collection criteria before data collection. The data collection process comprised three steps. First, a dental hygienist recorded the PCR score, PI score, and tongue coating score. Second, a structured questionnaire was administered by an interviewer. The entire interview process took approximately 30 minutes. Finally, the research staff collected data on masticatory performance, assessed according to the results of participants chewing color-changing gum, and on /pa/, /ta/, and /ka/ syllables and swallowing. The inter-rater reliability for two dental hygienists was kappa=0.89.

### *2.8 Statistical analysis*

Stata 13.1 (StataCorp LP, College Station, TX, USA) was used for statistical

analysis. A chi-square test and two sample t test were used to compare the demographic variables of the EG and CG. A logistic regression model using generalized estimating equations (GEEs) analyzed the change in oral self-care behaviors between baseline and the follow-ups. Comparisons of OHQoL, oral function index, and dental hygiene index between the EG and CG were analyzed with a linear regression model using GEEs. The effect size (Cohen's  $d$ ) of continuous variables were calculated from the mean difference between baseline and the follow-ups within the EG and CG. An effect of 0.20 is small, 0.50 is medium, and 0.80 is large [26].

The CONSORT flow chart of participant recruitment

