Therefore, the incidence of oral diseases (such as dental caries, periodontal disease, missing teeth, etc.) is higher than that of the general population [13-15]. Lay Health Advisors (LHAs) are chosen from the community; they share similar values, ethnic background, and socioeconomic status, and speak the same language as the people they serve. They are also known as natural helpers and are recommended to provide emotional and social services to local health institutions and communities [16-18]. Its advantages are to save manpower, money and reduce language and cultural barriers. LHA intervention strategies have been widely used in the community-based program, such as cancer screening, smoking cessation, risk behaviors, and the delivery of health information [19-23]. A recent study using an LHA strategy in aboriginal communities in Taiwan has proved more effective than reading leaflets alone for reducing barriers toward oral cancer screening and increasing self-efficacy for oral cancer self-examination [24]. Another study [25] conducting a community-level LHA program that addressed oral health disparities in the access and utilization of dental caries preventive services for immigrant children in Taiwan. A 4-week LHA intervention with one-on-one lessons and experience-sharing proved more effective in improving immigrant children's decay teeth, immigrant mothers' dental caries-related knowledge and maternal preventive behaviors than reading only the brochure.

Employing LHAs strategy can be effective in improving access to care and delivery of health care services for groups that have traditionally lacked access to adequate health care. Oral exercise (i.e., neck exercises, salivary gland massages, and vocal exercises) can effectively improve the oral diadochokinesis (DDK) rate and reduces xerostomia, dysphagia, and poor masticatory performance [9]. Early oral function intervention may be a valuable and actionable target for older adults to maintain quality of life. This is the first study to use the Lay Health Advisor (LHA) strategy to improve the oral function of the older adults in aboriginal communities. In

the present study, we aimed to evaluate the effectiveness of community-based oral exercise with LHA intervention on the oral health-related quality of life, oral function and oral self-care behaviors.

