## **METHODS**

### *2.1 Design*

A randomized controlled trial (RCT) was conducted. The participants recruited from aboriginal communities in Eastern Taiwan. Data collecting time was from 2019 to 2020. Participants from the identified communities were randomly assigned to EG or CG using random table.

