### *2.2 Participants*

Participants who were 55 years old or above and indigenous people were recruited in the present study. Participants who were disability, have had oral cancer, impaired facial appearance and impaired cognitive function were excluded. Impaired cognitive function was screening by Short Portable Mental Status Questionnaire (SPMSQ). Participants were recruited according to the predetermined minimal sample size estimated based on a type I error = 0.05, power = 0.95, and effect size (ES)  $f = 0.25$  (medium effect in Cohen's  $f$ ) [26]. The number of samples in each group was expected 66 participants. An additional 30% drop out rate was added. The final number of samples for each group were required at least 86 participants. The total sample size was 122 and 118 in EG and CG, respectively.

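### Nine to eleven outcomes are compared between arms with no designated primary outcome, primary follow-up, GEE treatment-effect term or multiplicity rule, so nothing fixes which result decides effectiveness

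*Combined protocol and SAP*

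**What the plan says.** The aim at the end of the Background is to evaluate effectiveness "on the oral health-related quality of life, oral function and oral self-care behaviors". It ranks none of these three domains and does not mention oral hygiene.

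Section 2.4 describes outcomes under four headings (quality of life, oral function, oral hygiene, self-care) and labels none as primary.

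Section 2.8 assigns the analyses. For the first three groups of outcomes: "Comparisons of OHQoL, oral function index, and dental hygiene index between the EG and CG were analyzed with a linear regression model using GEEs". For self-care, a logistic GEE "analyzed the change in oral self-care behaviors between baseline and the follow-ups"; no test between the arms is stated for these items.

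The only error rate is in section 2.2, a "predetermined minimal sample size estimated based on a type I error = 0.05, power = 0.95" with Cohen's f = 0.25, attached to no outcome, follow-up or test. It leads to this figure: "The number of samples in each group was expected 66 participants". The arms reported there are 122 (EG) and 118 (CG).

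**The concern.** The comparison of EG with CG is named, but four things that turn it into a decision are not: the outcome that counts, the follow-up that counts, the model term that is the treatment effect, and how several tests are to be handled together.

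The term matters. In a GEE fitted to baseline and follow-up data, a group coefficient and a group-by-time coefficient answer different questions. The follow-ups appear only in the plural, with none singled out.

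At stake is the conclusion the trial was run to reach. With no outcome designated, an analyst could follow section 2.8 faithfully, find a few of many outcomes below 0.05, and report effectiveness on those. The error rate of such a claim is not the 0.05 in section 2.2.

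**Working it through.** **Counting the outcomes under the linear GEE sentence**

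- Quality of life (2.4.1): GOHAI total, 1.
- Oral function (2.4.2): RSST, /pa/, /ta/, /ka/, gum colour, saliva flow, perceived dysphagia, 7. Section 2.4.2 counts the three syllables separately; section 2.3 lists DDK as one item, which gives 5.
- Oral hygiene (2.4.3): plaque control record, plaque index, tongue coating index, 3.

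By syllable: 1 + 7 + 3 = 11. Section 2.4.2 turns dysphagia into a yes/no classification, which does not obviously suit a linear model; leaving it out gives 10. Counting DDK once gives 1 + 5 + 3 = 9. Making both changes gives 8. A different restriction, the 11 less the 3 hygiene measures outside the stated aim, also gives 8.

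**Chance of at least one false positive**

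Inputs: alpha 0.05 from section 2.2, assumed two-sided; one test per outcome; all null hypotheses true.

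For k independent tests the chance is 1 − 0.95^k:

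- k = 9: 1 − 0.95^9 = 0.370
- k = 10: 1 − 0.95^10 = 0.401
- k = 11: 1 − 0.95^11 = 0.431

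For correlated tests I used normal test statistics with a common correlation ρ, rejecting at |Z| > 1.96. With c = 1.96, the chance is 1 − ∫ φ(x)[Φ((c − √ρ·x)/√(1−ρ)) − Φ((−c − √ρ·x)/√(1−ρ))]^k dx, integrated numerically. A simulation of 1,000,000 draws at k = 11, ρ = 0.7 gave 0.222, against 0.223 by integration. The documents give no correlations, so every ρ is an assumption and no row is a floor.

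| ρ (assumed) | k = 8 | k = 9 | k = 10 | k = 11 | k = 15 |
|---|---|---|---|---|---|
| 0 | 0.337 | 0.370 | 0.401 | 0.431 | 0.537 |
| 0.3 | 0.300 | 0.326 | 0.351 | 0.375 | 0.457 |
| 0.5 | 0.250 | 0.269 | 0.287 | 0.304 | 0.361 |
| 0.7 | 0.191 | 0.202 | 0.213 | 0.223 | 0.257 |
| 0.9 | 0.119 | 0.124 | 0.128 | 0.131 | 0.144 |

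The k = 15 column adds the four self-care items of section 2.4.4. It applies only if they too are compared between arms. Repeated testing over follow-ups is not counted anywhere in the table.

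**What section 2.2 reveals about the intended test**

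The plan's 66 per group can be reproduced, but not uniquely. For a repeated-measures group main effect with m measurements and correlation r between them, the noncentrality is f²·N·m/(1 + (m−1)r). With f = 0.25, alpha 0.05 and power 0.95, m = 4 and r = 0.5 give a multiplier of 4/2.5 = 1.6 and 66 per group. So do m = 2 and r = 0.25, since 2/1.25 = 1.6. The section states neither m nor r, so 66 does not identify the test.

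For a single two-group contrast, f = 0.25 corresponds to d = 0.5. At two-sided 0.05, 66 per group has power 0.81, 95% power needs 105 per group, and 122/118 has power 0.97. If 30% were lost (85/83), power would be about 0.90.

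**The case against.** The strongest reply is that the plan never says one significant outcome establishes effectiveness. The aim names several domains, and each can be reported at its own 5% level; whether a community education trial must adjust across domains is partly convention. This stands as far as it goes. A reader might infer that the trial has a 43% false-positive rate. The documents do not support that: the figure belongs to a decision rule they do not contain, with independent tests and the fullest count. What remains is that no other decision rule is given either.

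The count is also a reading. Section 2.8 names groups of outcomes, not 11 tests, and a common correlation is a simplification: the three syllable counts come from one test, and two of the hygiene measures both record plaque. Taking the word index literally, as one score per group, would leave three tests (1 − 0.95^3 = 14%), but sections 2.4.2 and 2.4.3 define no composite score. The choice among 9, 10 and 11 moves the result by a few points and does not remove it.

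A reader might also infer that 66 is wrong, that the trial was powered for a group main effect, or that it is underpowered. None follows. More than one set of unstated inputs gives 66, and the arms reported exceed what one contrast at d = 0.5 requires for 95% power before losses. The error rates above do not depend on the sample size.

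Finally, some pages and the figures were not available, and a figure may show the visit schedule. The point is therefore that the text seen designates no primary follow-up, not that no schedule exists.

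**Conclusion.** The concern holds in a limited form. The four omissions are confirmed in the text available, and they go beyond missing detail because the effectiveness conclusion is left resting on many unadjusted tests at 0.05.

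The size is conditional. If any significant outcome is taken to show effectiveness, the chance of at least one false positive with 9 to 11 outcomes is 37–43% under independence, 20–22% at ρ = 0.7 and 12–13% at ρ = 0.9. This assumes two-sided tests, one test per outcome and all nulls true. Even the smallest count and highest correlation examined (k = 8, ρ = 0.9) give 12%, still above 5%. The individual tests are not invalid. This is something the sponsor should correct, at little cost; it does not undermine the trial's data.

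**What to change.** 1. In sections 2.4 and 2.8, designate and justify one primary outcome at one named follow-up. GOHAI total is a candidate, being listed first in the aim and among the outcomes. An oral function measure could be justified instead: the Background calls this the "first study to use the Lay Health Advisor (LHA) strategy to improve the oral function of the older adults", and section 2.6 describes exercises "which will help speech and/or swallow functioning".
2. Test it with one between-group GEE contrast at two-sided 0.05: either group-by-time for change from baseline to that follow-up, or a baseline-adjusted group difference at that follow-up. State which, and base the effectiveness conclusion on it.
3. Test the other outcomes, including between-group tests of self-care, with Holm adjustment only if the primary is significant. Otherwise report them as exploratory, with confidence intervals and no effectiveness claim. Without this gate, two separate 5% families could together reach 1 − 0.95² = 9.75% if independent.
4. In section 2.2, state which contrast the 0.95 power refers to, with its inputs.
5. Section 2.1 says "Data collecting time was from 2019 to 2020". Date the designation, and label it post hoc if outcome data had already been seen.

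The cost is wording, one specified contrast and a restated power figure; no new data are needed. Some secondary results will no longer be called significant: on the count of 11, the first Holm step is 0.05/10 = 0.005 for the other ten outcomes, or 0.05/14 = 0.0036 with the four self-care items added. A post hoc designation carries less weight and cannot restore prespecification.

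### The only graded effect size, Cohen's d, is defined within each arm and without a named SD, so it does not measure the EG–CG difference

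*Combined protocol and SAP*

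**What the plan says.** Section 2.8 (Statistical analysis) handles continuous outcomes in two separate ways.

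- **Comparison of arms.** Quality of life, oral function and hygiene measures "between the EG and CG were analyzed with a linear regression model using GEEs". No standardised effect and no confidence interval is tied to this model.
- **Effect size.** Cohen's d is "calculated from the mean difference between baseline and the follow-ups within the EG and CG". The cut-offs follow at once: "An effect of 0.20 is small, 0.50 is medium, and 0.80 is large". No SD is named as the divisor, whether at baseline, pooled over time or of the change score.

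No other section defines a d for EG against CG. The only other effect size is the planning value in section 2.2, Cohen's f = 0.25, which does not define the reported d.

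Section 2.6 (Intervention) bears on how much change to expect in the CG. It states "All participants performed oral exercise before three meals a day", with the EG also receiving four LHA lessons, and it closes with "The participants in the CG received leaflets only".

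**The concern.** In a two-arm randomised trial, randomisation supports the contrast between arms. A baseline-to-follow-up change within one arm has no such protection. In the EG it contains whatever the lessons add, plus any time trend and any gain from repeating a performance task such as the saliva-swallowing test or the syllable-rate test. If the CG also exercised, it contains the effect of that exercise too.

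If *medium* or *large* is printed beside the EG's d, many readers will take it as the size of the LHA effect, and the plan does not warn against this. The distortion can go either way: improvement in the CG makes the EG's d overstate the added benefit, and deterioration in the CG makes it understate it. Without a named SD, the figure also cannot be reproduced or compared with other studies.

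**Working it through.** The documents give no outcome means, SDs, correlations or arm-level changes, so there is no stated d to reproduce. The inputs below are illustrative unless a section is cited.

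**1. Within-arm d against between-arm d.** With one common SD, between-arm d = (EG change − CG change)/SD = d(EG) − d(CG).

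| d(EG) | d(CG) | Between-arm d |
|---|---|---|
| 0.5 | 0.5 | 0.5 − 0.5 = 0 |
| 0.5 | 0.3 | 0.5 − 0.3 = 0.2 |
| 0.5 | 0.2 | 0.5 − 0.2 = 0.3 |
| 0.5 | 0 | 0.5 − 0 = 0.5 |

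The same *medium* EG value fits anything from no added effect to a medium one. Likewise, changes of 0.8 in the EG and 0.5 in the CG would be labelled *large* and *medium*, while the between-arm d is 0.8 − 0.5 = 0.3.

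**2. Choice of divisor.** With equal SDs at both times and pre-post correlation ρ, SD(change) = SD(baseline) × √(2(1 − ρ)). Take a mean change of 0.5 baseline SD, which is d = 0.50 on the baseline SD.

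| ρ (assumed) | √(2(1 − ρ)) | d on SD of change |
|---|---|---|
| 0.3 | 1.183 | 0.5/1.183 = 0.42 |
| 0.5 | 1.000 | 0.5/1.000 = 0.50 |
| 0.7 | 0.775 | 0.5/0.775 = 0.65 |
| 0.8 | 0.632 | 0.5/0.632 = 0.79 |

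The same data can fall below the medium cut-off or just short of the large one, depending only on a choice the plan leaves open.

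**3. Did the CG exercise?** The two statements in section 2.6 do not settle this and need to be reconciled. If the CG exercised, the shared exercise effect sits in the EG's d. If it did not, time and retest effects still do. The conclusion is the same either way.

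**4. Link to the planning effect (background only).** Section 2.2 gives f = 0.25, α = 0.05, power 0.95 and "The number of samples in each group was expected 66 participants". A one-way two-group comparison at f = 0.25 needs 105 per arm. A repeated-measures ANOVA test between groups with four measurements and correlation 0.5 gives exactly 66 (three measurements give 71, two give 79). That points to a between-arm effect, for which two equal arms give d = 2f = 0.50. The number of measurements and the correlation are assumptions, because section 2.2 names neither these nor the test.

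**5. Precision of a between-arm d.** Take ρ = 0.5, so that √(2(1 − ρ)) = 1, and treat the SD as known. Section 2.2 says "The total sample size was 122 and 118 in EG and CG, respectively".

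- No dropout, no clustering. Between arms: 1.96 × √(1/122 + 1/118) = 0.253. Within EG: 1.96 × √(1/122) = 0.177.
- 30% dropout, the rate allowed for in section 2.2, applied to those numbers gives 85.4 and 82.6. Assume an ICC of 0.05 by LHA, in the EG only, with participants spread evenly over the 28 certified LHAs of section 2.5: 85.4/28 = 3.05 per LHA and design effect 1 + 2.05 × 0.05 = 1.10. Between arms: 1.96 × √(1.10/85.4 + 1/82.6) = 0.310. Within EG: 1.96 × √(1.10/85.4) = 0.223.

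**The case against.** The strongest reply is that the plan already estimates the randomised contrast. The linear GEE gives an EG–CG difference on interpretable scales, such as 12 to 60 points for the GOHAI, and nothing in the document claims that the EG's d is the LHA effect. Both arms get a d, so the reader sees the CG's value beside the EG's. Within-arm standardised change is a legitimate descriptive statistic. This largely stands, and it is why the point is minor. It does not remove the defect: subtracting the two values gives a between-arm d only if both share one SD, which is not stated, and subtraction gives no interval.

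It can also be said that the sentence only describes what d is calculated from, so a single d contrasting the two changes is not excluded. The word *within*, applied to both arms, does not fit that reading naturally. If it was intended, the formula still has to be written down.

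Two further points are fair. Reproducing 66 per arm does not identify the design: other pairs of measurement number and correlation give the same variance factor. Four measurements at 0.5 give (1 + 3 × 0.5)/4 = 0.625, and two at 0.25 give (1 + 0.25)/2 = 0.625. The clustering figures rest wholly on assumed inputs, and section 2.2 does not say whether 122 and 118 are counted before or after dropout. The conclusion needs neither calculation.

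**Conclusion.** The concern holds and is of minor severity. As written, the plan attaches small, medium and large labels to a within-arm change with an unspecified divisor, and it attaches no standardised effect to the comparison that the trial randomised. That much rests on the text alone. How far the label would mislead cannot be computed from the documents; the figures above show only what is possible under a common SD and the stated range of correlations. No hypothesis test, sample size or decision depends on d. What is affected is how the size of benefit is reported, and whether it can be set against the planning effect if that was a between-arm one.

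**What to change.** For each continuous outcome and each follow-up, define d as the EG-minus-CG difference in change (or the baseline-adjusted difference) from the planned linear GEE, divided by a named SD such as the pooled baseline SD, and give a 95% CI. Apply the cut-offs to that d only. Keep the within-arm changes as descriptive rows.

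As a minimum, name the SD, say that the within-arm d is descriptive and is not the LHA effect, and print the unstandardised GEE difference with its 95% CI beside it.

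The cost is some analysis-plan wording and a few lines of code, with no new data. Section 2.1 dates data collection to 2019 to 2020, so the change falls on analysis and reporting. The price is that graded effects may be smaller and their intervals wider than the within-arm ones: on the illustrative inputs, a half-width of about 0.25 instead of 0.18, or 0.31 instead of 0.22 with dropout and clustering.
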